### **Subgroup analyses (all according to baseline values)**

Scheduled to perform following stratified analyses for the primary outcome:

- stratified analyzes in the presence of chronic lung disease or not
- stratified analyzes for QTc across the median
- stratified analyzes for < 2L nasal oxygen or ≥ 2L nasal oxygen
- stratified analyzes CRP < 50 mg/L and CRP ≥ 50 mg/L
- stratified analyzes D-dimer > 0.8 mg/L or D-dimer ≥ 0.8 mg/L

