### 3.3.6. Sample size:

#### Randomised controlled study

Prerequisite: Type 1 error rate = 5%. Power = 80%. Two-sided statistics. Group sequential design with one scheduled interim analysis after randomisation of 113 patients (50% recruitment).

Analysis: T-test.

Sample size is calculated based on the following estimates and indicative figures:

Expected duration of hospitalisation with COVID-19: 10 days

SD for "Days alive and discharged within 14 days" in patients with lung disease and COVID-19: 4 days (up to 10 days hospitalization)

Estimated time for improvement/deterioration: 1.5 days.

This requires 226 patients randomised 1:1 with 113 in each group. This is a fixed sample size. It is assumed that most patients complete the intervention.

However, for interim analysis, the Data and Safety Monitoring Board (DSMB) may recommend the steering committee to expand sample size.

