### **Sample size**

The power to avoid type II error is 80% (1- $\beta$ ) at a two-sided 5% significance level, using a t-test for the primary outcome, and a group-sequential design allowing for one interim analysis at half target recruitment. This provides a sample size of 226 subjects. All confidence intervals reported will be 95% confidence intervals.

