## **Figures and tables**

The first figure will be a Consolidated Standards of Reporting of Randomized Trials (CONSORT) flow chart. The second figure will be a Kaplan-Meier plot to describe the process of death by treatment arms. The third figure will be a forest plot illustrating all the preplanned sub analyses.

The first table will be the baseline characteristics of the ITT population. The second table will be of the primary and secondary outcomes according to the two groups and pair-wise comparisons.

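### The five subgroup factors are analysed only within separate strata; no treatment-by-subgroup interaction or between-strata difference is planned, so chance differences in significance could be misread as effect modification

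*SAP*

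**What the plan says.** The SAP section on subgroup analyses reads "Scheduled to perform following stratified analyses for the primary outcome" and lists five baseline factors: chronic lung disease (yes/no), QTc split at its median, nasal oxygen below 2 L or at least 2 L, CRP below 50 mg/L or at least 50 mg/L, and D-dimer. As printed, the D-dimer strata are above 0.8 mg/L and at or above 0.8 mg/L. They overlap, and values below 0.8 belong to neither.

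The SAP's figures section plans a "forest plot illustrating all the preplanned sub analyses". It does not say which statistics the plot will carry.

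Neither document mentions a treatment-by-subgroup term, a contrast between paired strata, a multiplicity rule for subgroups, or a rule for reading differences between strata. The adjusted primary model (SAP, primary objective and outcome) has main-effect covariates only. The protocol's only use of the word interaction concerns concomitant drugs.

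**The concern.** A subgroup analysis is usually meant to show whether the treatment effect differs between kinds of patient. Separate estimates in each stratum do not test that. If one stratum gives p < 0.05 and its partner does not, the two effects may still be identical, because each stratum holds only part of the sample and has much less power than the whole trial.

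The question matters here. Randomisation is stratified on chronic lung disease (protocol 3.3.2), and protocol 2.2 singles out patients with existing lung disease as a group who might benefit. A spurious contrast between strata could be carried into practice. Timing matters too: the SAP's blinding section rules out further analysis after unblinding unless a reviewer or editor asks for it. An interaction test not written down beforehand would therefore be post hoc.

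**Working it through.** **Inputs.** Protocol 3.3.6 gives "Type 1 error rate = 5%. Power = 80%. Two-sided statistics", a difference of 1.5 days ("Estimated time for improvement/deterioration: 1.5 days"), an SD of 4 days, and "This requires 226 patients randomised 1:1 with 113 in each group". The SAP sample-size section confirms the test: "using a t-test for the primary outcome".

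**Assumptions not in the documents.** Stratum prevalences are not given (only the QTc split is fixed, at the median), so 50/50, 30/70 and 20/80 are shown. An SD of 4 is taken to hold in every stratum, although the protocol gives it for patients with lung disease. The outcome is treated as normal, the interim look is ignored, and each stratum is assumed to be tested by t-test at two-sided 0.05, as for the primary outcome.

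**1. The plan's own figure.** Normal approximation: n per arm = 2(1.960 + 0.842)² × 4² / 1.5² = 111.6, so 112. The exact t-test gives 112.6, so 113 per arm and 226 in total, with power 80.1%. The stated size is reproduced.

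**2. Same 1.5-day effect in everyone.** With n patients per arm in a stratum, SE = 4√(2/n) and power ≈ Φ(1.5/SE − 1.960). At 50/50, n = 113 × 0.5 = 56.5, SE = 0.753 and power = 51%. The two strata of one factor contain different patients, so P(exactly one significant) = p₁(1 − p₂) + p₂(1 − p₁).

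| Split | Power in each stratum | Exactly one significant |
|---|---|---|
| 50/50 | 0.513, 0.513 | 2 × 0.513 × 0.487 = 0.50 |
| 30/70 | 0.339, 0.655 | 0.339 × 0.345 + 0.655 × 0.661 = 0.55 |
| 20/80 | 0.243, 0.713 | 0.243 × 0.287 + 0.713 × 0.757 = 0.61 |

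A simulation of 6,000 trials (226 patients, five mutually independent 50/50 factors) gave 49% for one pair. At least one of the five pairs was discordant in 83% of trials, with no effect modification present.

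**3. No effect in anyone.** One pair is discordant with probability 2 × 0.05 × 0.95 = 9.5%. Across all five factors, the same simulation gave at least one significant stratum in 29% of trials.

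**4. What an interaction test would do.** SE of the difference between strata = 4√(2/n₁ + 2/n₂).

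| Split | SE (days) | Power at 1.5 days | Power at 3.0 days | Detectable with 80% power |
|---|---|---|---|---|
| 50/50 | 1.06 | 29% | 80% | 2.98 days |
| 30/70 | 1.16 | 25% | 73% | 3.25 days |
| 20/80 | 1.33 | 20% | 62% | 3.73 days |

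The false-flag rate is about 5% per factor whether the common effect is 0 or 1.5 days (simulated 5.2% and 4.9%). Over five uncorrected tests it is 1 − 0.95⁵ = 22.6% (simulated 22.6% and 22.3%).

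**The case against.** The subgroups are prespecified, few, defined at baseline and confined to the primary outcome. Nothing in the SAP says the sponsor will compare significant with non-significant strata. A reader might infer that false subgroup claims will follow, but the documents only leave that reading open: they state no within-stratum test and no interpretation rule.

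A reader might also infer that the plan cannot show whether effects differ. That goes too far. If the forest plot shows each stratum's estimate with its 95% CI (the level the SAP sets for all intervals), the difference and its standard error follow by arithmetic for any valid pair of strata. What is missing is a planned contrast, not the information. Protocol 2.2 can moreover be read as asking whether treatment works in lung disease, which the stratum estimate addresses directly.

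A third tempting step is 1 − 0.95¹⁰ = 40% for at least one significant stratum under no effect. That treats ten strata as independent, but the SAP cuts the same 226 patients five ways. The simulated figure is about 29%, and it would be lower if oxygen need, CRP and D-dimer are correlated.

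Finally, on the no-effect yardstick the remedy gains little: about 23% against about 29%. That is correct, and it is why the exploratory label belongs in the fix. The larger gain comes when there is a common effect: about 5% false flags per factor, against about 50% discordant pairs.

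**Conclusion.** The point holds as a gap in the secondary analyses. The SAP plans within-stratum analyses and a plot, and no contrast between strata, so differences in significance could be misread as effect modification. With a uniform 1.5-day effect, about 50% of trials would show a discordant pair for any one factor at a 50/50 split, rising to about 61% at 20/80. With no effect, about 29% would show at least one significant stratum. The first figures rest on the protocol's effect and SD and on assumed splits. The 29% also needs five mutually independent factors.

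The harm is to interpretation only. The primary comparison, its error rate and N = 226 are not affected. The change is worth making before unblinding, but the main result does not depend on it.

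**What to change.** Amend the SAP's subgroup section before the allocation code is broken:

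- Correct the D-dimer cut so that the two strata are exclusive and cover all values. Until then the fifth term cannot be fitted.
- For each factor, fit a linear model of DAOH14 on treatment, subgroup and their interaction. If the SAP's rule moves reporting to 21 days, use that outcome.
- On the forest plot, show the interaction estimate (difference in effect between strata) with 95% CI and p-value beside the stratum estimates.
- State that any claim of differing effects rests on the interaction and not on significance within a stratum.
- Label the analyses exploratory, noting the 23% chance of at least one false flag over five uncorrected tests and the 29% power for a 1.5-day interaction at a 50/50 split. A non-significant interaction should not be reported as evidence that effects are equal.

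The cost is a few sentences and five model terms, within the general linear model framework the SAP already uses, with no new data. The downside is that the interaction estimates will be imprecise; their CIs will show this.

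### The D-dimer subgroup is defined as > 0.8 versus ≥ 0.8 mg/L, so the two strata overlap almost completely and patients below 0.8 mg/L belong to neither

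*SAP*

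**What the plan says.** The SAP section on subgroup analyses, which are all based on baseline values, opens with "Scheduled to perform following stratified analyses for the primary outcome" and lists five splits: chronic lung disease, QTc at the median, nasal oxygen, CRP and D-dimer. The D-dimer line reads "stratified analyzes D-dimer > 0.8 mg/L or D-dimer ≥ 0.8 mg/L".

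The two lines directly above it are built differently. The oxygen line is "stratified analyzes for < 2L nasal oxygen or ≥ 2L nasal oxygen" and the CRP line is "stratified analyzes CRP < 50 mg/L and CRP ≥ 50 mg/L". Each pairs a strictly-below condition with an at-or-above condition.

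The results are to be displayed. Under Figures and tables the SAP states: "The third figure will be a forest plot illustrating all the preplanned sub analyses".

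D-dimer also appears in the protocol's blood-test lists (section 3.3.3, in the notes on blood samples, and section 5) and in the SAP's biochemistry list, each time as a measured variable without a cut-off.

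**The concern.** A stratified analysis needs strata that do not overlap and that together cover the patients being analysed. The D-dimer line meets neither condition, because both of its conditions are on the high side of the same threshold.

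If the line is programmed literally, the forest plot has two D-dimer rows drawn from almost the same patients and no row for low D-dimer. The two estimates would agree closely whether or not D-dimer modifies the treatment effect, and a reader could take that agreement as evidence of a consistent effect. The question behind the subgroup would go unanswered.

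Timing also matters. The SAP's introduction gives the prevention of data-driven results as a reason for fixing the plan in advance. Its section on blinding says that, once allocation is unblinded, no further analysis follows unless a reviewer or editor asks for it. An error noticed late is therefore awkward to repair within the plan's own rules.

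**Working it through.** **Background figure.** The check does not depend on the sample size, but the total of 226 is used below for scale, so it was reproduced first. Inputs from protocol section 3.3.6: "Type 1 error rate = 5%. Power = 80%. Two-sided statistics"; SD "4 days (up to 10 days hospitalization"); "Estimated time for improvement/deterioration: 1.5 days".

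- Normal approximation: n per arm = 2 × (1.960 + 0.842)² × 4² / 1.5² ≈ 111.6, rounded up to 112 (224 in total).
- Exact t-test: 112.6 per arm, rounded up to 113, giving 226. This matches the protocol. Power at 113 per arm is 80.1%.

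**Set logic, as written.** Let x be the baseline D-dimer in mg/L, with A = {x > 0.8} and B = {x ≥ 0.8}.

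- A ∩ B = A, so stratum A lies entirely within stratum B.
- B without A = {x = 0.8}, the only patients who distinguish the two rows.
- Outside both = {x < 0.8}, that is, everyone below the threshold.

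**Test values, as written and with the first sign reversed:**

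| D-dimer (mg/L) | In > 0.8 | In ≥ 0.8 | As written | With < 0.8 and ≥ 0.8 |
|---|---|---|---|---|
| 0.2 | no | no | omitted | low |
| 0.5 | no | no | omitted | low |
| 0.79 | no | no | omitted | low |
| 0.8 | no | yes | one stratum | high |
| 0.81 | yes | yes | both strata | high |
| 1.5 | yes | yes | both strata | high |

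With the sign reversed, each value falls in exactly one stratum.

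**Scale.** The documents give no D-dimer distribution, so the share p of patients below 0.8 mg/L has to be assumed. Omitted ≈ 226 × p. In both strata ≈ 226 × (1 − p), apart from any patients at exactly 0.8 and taking every patient to have a baseline value.

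| Assumed p | Omitted | In both strata |
|---|---|---|
| 30% | 68 | 158 |
| 50% | 113 | 113 |
| 70% | 158 | 68 |

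**The case against.** The strongest reply is that this is an obvious slip. The variable, the threshold, the baseline timing and the outcome are all specified, and the neighbouring lines show what was meant. An analyst who coded two inequalities in the same direction would probably notice. The two one-symbol repairs (< 0.8 with ≥ 0.8, or > 0.8 with ≤ 0.8) differ only for patients at exactly 0.8 mg/L, so there is almost no room for a data-driven choice. The SAP also has all analyses done on arms labelled A and B before the code is broken, so even a correction after data release could be made without knowledge of allocation. Finally, the text was extracted from a PDF, and the point rests on one symbol.

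Much of this stands, and it limits the importance. The omitted patients remain in the intention-to-treat population, the primary and secondary analyses and, given the relevant baseline data, the other four subgroups. No power, alpha or decision rule is attached to the D-dimer split. A late correction that is documented and made blind to allocation would do little damage.

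The reply does not make the definition correct. A meaning inferred from adjacent lines is not a stated definition, and this line is an operative rule for a figure the plan commits to. A misread symbol is possible but unlikely, since the less-than sign was read correctly in the two lines just above. The source file will settle it.

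**Conclusion.** The concern holds as stated. As written, the first D-dimer stratum is a subset of the second, they differ only at exactly 0.8 mg/L, and all patients below 0.8 mg/L are left out of this subgroup analysis. That follows from the inequalities alone. Only the patient counts rest on an assumption: roughly 68 to 158 of 226 omitted if 30% to 70% are below the cut-off.

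The consequence is confined to one of five subgroup analyses and its rows in the forest plot. The primary estimate, the type I error rate and the sample size are unaffected. It should be corrected, but it does not threaten the trial's main conclusion.

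**What to change.** Check the source file. If the sign is as extracted, change the first D-dimer condition from > to <, so that the strata are < 0.8 mg/L and ≥ 0.8 mg/L, in the same form as the oxygen and CRP lines. Record this as a dated correction to the SAP before the database is accessed. The strata are then mutually exclusive and cover every patient with a baseline D-dimer value.

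The cost is one character and a line in the SAP's change record. Sample size, data collection and all other analyses stay as they are. If the error comes to light only after data release, the correction should be made before the randomisation code is broken and reported as such.

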## **Figures and tables**

The first figure will be a Consolidated Standards of Reporting of Randomized Trials (CONSORT) flow chart. The second figure will be a Kaplan-Meier plot to describe the process of death by treatment arms. The third figure will be a forest plot illustrating all the preplanned sub analyses.

The first table will be the baseline characteristics of the ITT population. The second table will be of the primary and secondary outcomes according to the two groups and pair-wise comparisons.

## **Funding**

The trial was funding by Novo Nordisk Foundation with 2.2 million Dkr. No medical company is supporting this trial. The funding sources will have no influence on trial design, data collection, analysis, or reporting.

**Approved by:** Ethics Committees of all participating sides (H-20022574) and the Danish Medicines Agency (EudraCT no: 2020-001198-55) and the Danish Data Protection Agency (2020-256).

## **Acknowledgements**

The Steering Committee of COP:TRIN for input and advice during the trial recruitment.

## **Competing interests**

The authors declare that they have no competing interests.

## **Abbreviations**

AECOPD Acute exacerbations of chronic obstructive pulmonary disease

ANOVA Analysis of variance

CAT COPD Assessment Test

CONSORT Consolidated Standards of Reporting of Randomised Trials

DAOH Days alive and out of hospital

FEV1 Forced expiratory volume in 1 second

GCP Good Clinical Practice

ICH International Conference on Harmonisation

ITT Intention-to-treat

IQR Interquartile range

